6.4.1.3. Nonresponder Imputation

The nonresponder imputation (NRI) method will be used to handle missing data relative to the supportive estimand for categorical endpoints (composite). Patients who receive rescue medication (per Protocol Section 6.3), or discontinue treatment, will be set to non-response subsequent to this time through Week 16. Intermittent missing values will also be set to non-response.

The nonresponder imputation (NRI) method imputes missing values as non-responders and can be justified based on the composite strategy (ICH E9R1) for handling intercurrent events. In this strategy patients are defined as responders only if they meet the clinical requirements for response at the predefined time AND they remain on the assigned study treatment (ie not using rescue medications and not having missing values due to other reasons). Failing either criteria by definition makes them nonresponders.

Randomized patients without at least 1 postbaseline observation will also be defined as nonresponders for all visits for the NRI analysis.

6.4.1.4. Last Observation Carried Forward (LOCF)

In this analysis, the values subsequent to rescue medication use (per Protocol Section 6.3) or treatment discontinuation will be made missing. All missing values will be imputed using LOCF. Baseline value will be used for imputation if there is no postbaseline observation.

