2.3. Other Secondary Endpoints

- Proportion of patients with EASI-75, EASI-90 and EASI-50 by visit
- Proportion of patients with IGA Score of 0 or 1 and a reduction ≥ 2 points from Baseline by visit
- Percentage change from Baseline in EASI Score by visit
- Percentage change from Baseline in Pruritus NRS by visit
- Percentage of patients with Pruritus NRS change of ≥ 4 from Baseline by visit
- Percentage of patients with a Pruritus NRS score of ≥ 4 points at Baseline who achieve a ≥ 4 -point reduction from Baseline by visit
- Change from Baseline in Sleep-Loss score by visit
- Change from Baseline in DLQI/CDLQI by visit
- Change from Baseline in EQ5D by visit

- Change from Baseline in POEM by visit
- Change from Baseline in PROMIS Anxiety measure by visit
- Change from Baseline in PROMIS Depression measure by visit
- Change in ACQ-5 score from Baseline to Week 16 in patients who have self-reported comorbid asthma
- Percentage change from Baseline to Week 16 in SCORAD

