7.10. Week 16 (\pm 3 Days) Transition to Maintenance Period

- Administer the DLQI/CDLQI, and EQ-5D
- Administer the PROMIS measures
- Collect ACQ-5 for patients with comorbid asthma
- Complete the following assessments: IGA, BSA, EASI and SCORAD
- Perform a complete physical examination, including height and weight
- Review and record AEs and update concomitant medication and procedure/therapy information
- Review compliance report on the eDiary, confirm moisturizer use and remind patient to record the following: Pruritus and Sleep-Loss (daily), and POEM (weekly)
- Measure vital signs
- Draw pre-dose blood samples for laboratory tests, PK and ADA testing
- Collect a urine sample for urinalysis
- Conduct urine pregnancy test (WOCBP only)
- Re-randomize the patient to the Maintenance Period
- Train the patient to self-administer study drug
- Administer one injection and observe the patient self-injecting
- Dispense study drug for Week 18 injections

Sites collecting photos will also:

- Obtain a photograph of the target lesion

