6.2.1.3. Supportive Estimand for Continuous Endpoints (Hypothetical)

The supportive estimand for continuous endpoints is a hypothetical estimand representing the supportive clinical question of interest: what is the difference between treatment conditions in the target patient population, in means after 16 weeks if rescue medication was not available and all patients adhered to the treatment?

The supportive estimand is described by the following attributes:

- A. Population: defined through appropriate I/E criteria to reflect the targeted patient population for approval
- B. Endpoint: apply to continuous endpoints
- C. How to account for intercurrent events (ICEs)
 - a. For subjects who require any use of rescue medication or discontinue treatment prior to week 16, a hypothetical strategy will be used to estimate what the treatment effect would have been if rescue medication was not available, and all subjects adhered to the treatment. Therefore, hypothetical strategy is used for these types of ICEs.
- D. Population-level summary: difference in means between treatment conditions

Analytical details on how missing data including those as a result of intercurrent events will be handled for Induction Period can be found in Section [6.4.1](#). Detailed analyses relative to

estimands including analysis type, method and imputation, population, time point, and treatment comparisons for efficacy/health outcomes analyses can be found in Section 6.11.

The following table (Table KGAC.6.3) summarizes the analytical strategies that will be conducted on the intercurrent events for the three estimands.

Table KGAC.6.3. Description of Primary and Supportive Estimands for Induction Period

Estimand	Analysis Strategy for Intercurrent Events			Missing Data Imputation Method	
	Rescue Medication	Treatment Discontinuation			
		Due to lack of efficacy	Due to any other reasons		
Primary Estimand (Hybrid)	Composite: Set to baseline	Composite: Set to baseline	Hypothetical: Set to missing	Primary analysis: MCMC-MI Sensitivity analysis: tipping point analysis	
Supportive Estimand for Categorical Endpoints (Composite)	Composite: Set to non-responder	Composite: Set to non-responder	Composite: Set to non-responder	NRI	
Supportive Estimand for Continuous Endpoints (Hypothetical)	Hypothetical: Set to missing	Hypothetical: Set to missing	Hypothetical: Set to missing	MMRM, LOCF	

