6.4.1. Handling of Dropouts or Missing Data for Induction Period

For efficacy analysis relative to the primary estimand, the primary method of handling missing data including those as a result of intercurrent events will be based on Markov Chain Monte Carlo Multiple Imputation (MCMC-MI). The description of MCMC-MI method can be found in Section [6.4.1.1](#). Tipping point analysis as described in Section [6.4.1.2](#) will serve as the sensitivity analysis for the primary analysis.

For efficacy analysis relative to the supportive estimand for categorical endpoints, missing data including those as a result of intercurrent events will be imputed as non-responder. The description of non-responder imputation (NRI) can be found in Section [6.4.1.3](#).

For efficacy analysis relative to the supportive estimand for continuous endpoints collected only once post-baseline, missing data including those as a result of intercurrent events will be imputed using Last Observation Carried Forward (LOCF). The description of LOCF can be found in Section [6.4.1.4](#).

For efficacy analysis relative to the supportive estimand for continuous endpoints collected multiple times post-baseline, a Mixed Model for Repeated Measures (MMRM) will be performed without explicit imputation. The description of MMRM can be found in Section [6.4.1.5](#).

Table KGAC.6.6 describes the planned imputation methods for efficacy and health outcome endpoints for Induction Period.

Table KGAC.6.6. Imputation Techniques for Various Variables During Induction Period

Type of Endpoints	Efficacy and Health Outcome Endpoints	Estimand (Analysis strategy for Intercurrent Events)	Missing Data Imputation Method (Analysis Method)
Categorical	IGA, EASI, Pruritus NRS, sleep loss and DLQI related categorical endpoints at pre-specified timepoints	Primary Estimand (Hybrid)	MCMC-MI, Tipping point analysis (CMH)
		Supportive Estimand (Composite)	NRI (CMH)
	Remaining categorical endpoints	Supportive Estimand (Composite)	NRI (CMH)
Continuous	EASI percent change, Pruritus NRS percent change, Sleep loss change from baseline, DLQI change from baseline	Primary Estimand (Hybrid)	MCMC-MI (ANCOVA)
		Supportive Estimand (Hypothetical)	No imputation (MMRM)
	Remaining continuous endpoints collected at multiple post-baseline timepoints including BSA, POEM and CDLQI	Supportive Estimand (Hypothetical)	No imputation (MMRM)

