	Remaining continuous endpoints collected only once post-baseline	Supportive Estimand (Hypothetical)	LOCF (ANCOVA)

Abbreviations: ANCOVA = analysis of covariance; CMH = Cochran-Mantel-Haenszel; EASI = Eczema Area and Severity Index; IGA = Investigator's Global Assessment for AD; LOCF = last observation carried forward; MCMC-MI = Markov chain Monte Carlo multiple imputation; MMRM = mixed-model repeated measures; NRI = Nonresponder Imputation; NRS = Numeric Rating Scale.

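### For change scores scheduled once after baseline in induction, the SAP's LOCF rule normally assigns zero change, which does not estimate the hypothetical estimand the analysis is assigned to

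*SAP*

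**What the plan says.** **Estimand.** SAP 6.2.1.3 asks for the difference "in means after 16 weeks if rescue medication was not available and all patients adhered to the treatment". Table KGAC.6.3 implements this by setting values to missing after rescue and after discontinuation for any reason.

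**Method.** SAP 6.4.1 sends "continuous endpoints collected only once post-baseline" to LOCF, and Table KGAC.6.6 pairs that with ANCOVA. Table KGAC.6.12 confirms it for change and percent change in SCORAD, and for change in EQ-5D VAS and both index scores, PROMIS Anxiety and Depression, and ACQ-5.

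**Imputation rule.** SAP 6.4.1.4 states: "In this analysis, the values subsequent to rescue medication use (per Protocol Section 6.3) or treatment discontinuation will be made missing". All missing values are then filled by LOCF, with the fallback "Baseline value will be used for imputation if there is no postbaseline observation".

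**Schedule.** At Week 16 the protocol (Section 7.10) says "Complete the following assessments: IGA, BSA, EASI and SCORAD", and it also collects EQ-5D, PROMIS and ACQ-5. Sections 7.3 to 7.9 (Weeks 2 to 14) list none of these four. The early-termination visit (Section 7.20) collects all four.

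**Status.** These are other secondary endpoints, for example "Percentage change from Baseline to Week 16 in SCORAD" (Protocol 2.3).

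**The concern.** With one scheduled post-baseline value there is normally no earlier observation to carry forward. LOCF then reduces to baseline carried forward: the patient is counted as not having changed. The estimand asks what the mean would have been "if rescue medication was not available and all patients adhered to the treatment". Zero change answers that only if the affected patients would, on average, not have changed, and neither document argues that they would not.

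The SAP's own labels conflict. In Table KGAC.6.3, setting to baseline after rescue or lack of efficacy is called composite under the primary estimand. For the single-visit endpoints the same result is reached under the hypothetical label, and it extends to discontinuation for other reasons and to plain missed visits. BSA, POEM and CDLQI target the same hypothetical estimand through MMRM, which assumes missing at random (SAP 6.4.1.5). The visit schedule alone decides which assumption an endpoint receives.

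At stake are the arm means and treatment differences reported for these change scores. As a single imputation, the rule also carries no imputation uncertainty into the standard error.

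**Working it through.** **1. Trace the rule by type of patient.**
- Rescued, attends Week 16 (Protocol 6.3 keeps patients on systemic rescue attending): the observed score is deleted and baseline inserted. An unscheduled visit for a flare requires IGA, BSA and EASI only (Protocol 7.22), so normally no SCORAD exists from before rescue.
- Stops study drug, attends an early-termination visit (Protocol 8.7.2): the instruments are collected, but after discontinuation, so 6.4.1.4 read literally deletes them. SAP 6.1.2 says unscheduled assessments still feed LOCF change analyses. The SAP does not say which rule governs.
- No rescue, on drug, misses Week 16 (SAP 6.16.1 treats pandemic-related gaps like any other): baseline is inserted.

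**2. Effect on the estimate.** Let d_t and d_p be the shares of lebrikizumab and placebo patients with a deleted or missing Week 16 value, and h_t and h_p the mean changes those patients would have had under the hypothetical condition. Replacing these by zero gives

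bias = -(d_t × h_t - d_p × h_p).

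The documents give none of these four quantities. Everything below is illustrative, for SCORAD percent change, with assumed full-arm means m_t = -55 and m_p = -25 (true difference -30).

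**3. Events unrelated to outcome** (h equals the arm mean): expected estimate = (1 - d_t) × m_t - (1 - d_p) × m_p.

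| d_t / d_p | Calculation | Estimate | Bias |
|---|---|---|---|
| 5% / 5% | -52.25 + 23.75 | -28.5 | +1.5 |
| 10% / 10% | -49.5 + 22.5 | -27.0 | +3.0 |
| 20% / 20% | -44.0 + 20.0 | -24.0 | +6.0 |
| 10% / 30% | -49.5 + 17.5 | -32.0 | -2.0 |
| 10% / 40% | -49.5 + 15.0 | -34.5 | -4.5 |

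The effect shrinks when d_p/d_t is below m_t/m_p = 55/25 = 2.2 and grows above it. Over the same event rates, means of -50 and -30 (true -20) give -16.0 to -27.0, and means of -60 and -20 (true -40) give -32.0 to -42.0.

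**4. Events tied to poor response.** This is a simulation with 267 versus 133 patients (2:1, about 400) and 400 replicates. Week 8 EASI change = 0.7 × arm mean + patient effect (SD 20) + noise (SD 12). Week 16 SCORAD change = arm mean + the same patient effect + noise (SD 12). The event occurs when Week 8 EASI change is worse than a cut-off.

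| Cut-off | Event rates | True | Baseline carried | Observed cases only | Within-arm imputation from Week 8 EASI |
|---|---|---|---|---|---|
| -10% | 10.9% / 37.2% | -29.84 | -29.87 | -23.06 | -29.71 |
| 0% | 4.9% / 22.9% | -30.07 | -29.63 | -25.14 | -30.05 |
| +10% | 1.8% / 12.0% | -29.90 | -29.15 | -26.71 | -29.85 |
| +20% | 0.6% / 5.4% | -29.95 | -29.37 | -28.25 | -29.94 |

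The bias in the difference is 0 to 0.8 points.

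**5. Why the first row is so small.** Week 8 EASI has SD √(400 + 144) = 23.3, and the slope of Week 16 on it is 400/544 = 0.735. At the -10% cut-off, z = (-10 + 38.5)/23.3 = 1.22 on lebrikizumab and (-10 + 17.5)/23.3 = 0.32 on placebo. Then h = m + 0.735 × 23.3 × φ(z)/(1 - Φ(z)), giving h_t = -25.75 with d_t = 0.111, and h_p = -7.62 with d_p = 0.374. The arm errors are 0.111 × 25.75 = 2.86 and 0.374 × 7.62 = 2.85 points. Each arm mean is off by nearly 3 points, and the errors cancel in the difference.

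**The case against.** The strongest reply is that the practical effect may be negligible. Protocol 6.3 ties induction rescue to intolerable symptoms, so affected patients are plausibly poor responders, for whom zero change is a fair approximation. Step 4 supports this for the treatment difference. It does not make the label correct, and step 5 shows that part of the agreement can be cancellation while both arm means are wrong.

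The early-termination visit is a real qualification. If half the affected patients had a usable value equal to their hypothetical Week 16 value, the biases in step 3 would halve (6.0 to 3.0, and -4.5 to -2.25). But SAP 6.4.1.4 taken literally removes those values, and a value from mid-course is not a Week 16 value.

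Three stronger readings are tempting, and the documents do not support them:
- A reader might infer that the rule favours lebrikizumab because placebo patients will be rescued or drop out more often. Neither document gives event rates, and even with more events on placebo the direction depends on how those patients would have fared.
- A reader might infer that these instruments have no other planned analysis. Table KGAC.6.12 also plans SCORAD75, SCORAD90 and the EQ-5D no-problem proportions with non-responder imputation. The statement is true only of the continuous change scores.
- A reader might infer that the main efficacy conclusions are exposed. Primary, co-primary and major secondary endpoints use MCMC multiple imputation under the primary estimand.

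**Conclusion.** The mismatch stands on the SAP's text. For SCORAD, EQ-5D VAS and index, PROMIS and ACQ-5 change scores in induction, a deleted or missing Week 16 value normally becomes zero change, so the analysis does not estimate the hypothetical estimand in 6.2.1.3. The unresolved exception is the early-termination value.

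No size or direction can be asserted. With assumed means of -55% and -25%, the error in a 30-point difference runs from 6 points toward the null to 4.5 points away from it when events are unrelated to outcome, and is 0 to 0.8 points when events follow poor response. These figures rest on assumed means, event rates and normal models, and apply to SCORAD percent change. The other instruments follow the same formula on their own scales.

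The reach is limited to other secondary endpoints outside both regulators' multiplicity schemes. This is a point to correct before reporting, and it does not threaten the trial's main claims.

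**What to change.** In SAP 6.4.1, 6.4.1.4 and Tables KGAC.6.3, KGAC.6.6 and KGAC.6.12, do one of the following for the row "Remaining continuous endpoints collected only once post-baseline":

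- **(a) Relabel.** Call the analysis composite, baseline carried forward, and remove it from the hypothetical estimand. This costs only wording.
- **(b) Estimate the stated estimand.** Impute Week 16 within arm by multiple imputation from the endpoint's own baseline and the on-treatment data before the event (EASI, IGA, BSA, pruritus and POEM for the skin and quality-of-life measures), then run ANCOVA and combine. For ACQ-5 the skin measures are not obvious predictors, so use its own baseline and other relevant covariates, or relabel it under (a).

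Simply dropping LOCF is not enough. With one post-baseline visit MMRM reduces to ANCOVA on observed cases, which gave -23.1 to -28.3 against about -30 in the simulation.

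Under either option, reconcile SAP 6.1.2 with 6.4.1.4: state whether an early-termination value is deleted or carried forward, and by what date rule.

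Option (b) needs no new data, but it is more than reuse of existing code. The current model in 6.4.1.1 uses the endpoint's relevant baseline and post-baseline values, so a cross-instrument model and new seeds are needed, and it relies on missing at random. Because SAP Version 5 was approved after the study team was unblinded to induction treatment, add it as a dated supplementary analysis and disclose it as such in the CSR.

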6.4.1.5. Mixed-effects Model for Repeated Measures

Mixed Model for Repeated Measures analyses will be performed on continuous endpoints to mitigate the impact of missing data. This approach assumes missing observations are missing-at-random (missingness is related to observed data) and borrows information from patients in the same treatment arm taking into account both the missingness of data through the correlation of the repeated measurements.

When MMRM is used, the model includes treatment, baseline value, visit, the interaction of the baseline value-by-visit, the interaction of treatment-by-visit, and the stratification factors mentioned in Section 6.3 as fixed factors. The covariance structure to model the within-patient errors will be unstructured.

6.4.2. Handling of Dropouts or Missing Data for Maintenance Period

For maintenance efficacy analysis relative to the maintenance primary estimand, the method of handling missing data including those as a result of intercurrent events will be Markov Chain Monte Carlo Multiple Imputation (MCMC-MI). The description of maintenance MCMC-MI method can be found in Section 6.4.2.1.

MCMC-MI will also be used to handle missing data relative to the maintenance supportive estimand (Hybrid) as described in Section 6.4.2.1.

For efficacy analysis relative to the maintenance supportive estimand for categorical endpoints (Composite), missing data including those as a result of intercurrent events will be imputed as non-responder. The description of maintenance non-responder imputation (NRI) can be found in Section 6.4.2.2.

For efficacy analysis relative to the maintenance supportive estimand for continuous endpoints (Hypothetical), missing data including those as a result of intercurrent events will be imputed using Last Observation Carried Forward (LOCF). The description of maintenance LOCF can be found in Section 6.4.2.3.

Table KGAC.6.9 describes the planned imputation methods for efficacy and health outcome endpoints for Maintenance Period.

Table KGAC.6.9. Imputation Techniques for Various Variables During Maintenance Period

Type of Endpoints	Efficacy and Health Outcome Endpoints	Estimand (Analysis strategy for Intercurrent Events)	Missing Data Imputation Method (Analysis Method)
Categorical	IGA, EASI, and Pruritus NRS related categorical endpoints at pre-specified timepoints	Maintenance Primary Estimand (Hybrid)	MCMC-MI (CMH)
		Maintenance Supportive Estimand (Hybrid)	MCMC-MI (CMH)
		Maintenance Supportive Estimand (Composite)	NRI (CMH)
	Remaining categorical endpoints	Maintenance Supportive Estimand (Composite)	NRI (CMH)
Continuous	EASI percent change, Pruritus NRS percent change	Maintenance Primary Estimand (Hybrid)	MCMC-MI (ANCOVA)
		Maintenance Supportive Estimand (Hybrid)	MCMC-MI (ANCOVA)
		Maintenance Supportive Estimand (Hypothetical)	LOCF (ANCOVA)
	Remaining continuous endpoints	Maintenance Supportive Estimand (Hypothetical)	LOCF (ANCOVA)

Abbreviations: ANCOVA = analysis of covariance; CMH = Cochran-Mantel-Haenszel; EASI = Eczema Area and Severity Index; IGA = Investigator's Global Assessment for AD; LOCF = last observation carried forward; MCMC-MI = Markov chain Monte Carlo multiple imputation; MMRM = mixed-model repeated measures; NRI = Nonresponder Imputation; NRS = Numeric Rating Scale.

6.4.2.1. Maintenance Period MCMC-MI

The MCMC-MI will be used to handle missing data relative to the maintenance primary estimand (Hybrid) and maintenance supportive estimand (Hybrid) for both binary and continuous endpoints. Imputation will be conducted within each treatment group independently so the pattern of missing observations in one treatment group cannot influence missing value imputation in another. The SAS PROC MI with MCMC option will be used to conduct the MCMC-MI. The imputation model will include the relevant baseline and post-baseline.

For each imputation process, 25 datasets with imputations will be calculated. The initial seed values are given in [Table KGAC.6.7](#). Each complete data set will be analyzed with the specified analysis. The results from these analyses will be combined into a single inference using SAS PROC MIANALYZE.

Cochran-Mantel-Haenszel (CMH) test statistic will be transformed using the Wilson-Hilferty transformation and then standardized (Ratitch 2013) prior to combining them using SAS PROC

MIANALYZE. Details of combining estimates and test statistics for categorial endpoints with multiple imputation can be found in [Appendix 2](#).

The imputation and analysis will be conducted on the Modified Maintenance Primary Population only.

The derivation of binary responses related to EASI, IGA and Pruritus NRS for Maintenance Period will follow the derivation for Induction Period.

Table KGAC.6.10. Seed Values for MCMC-MI for Maintenance Period

Analysis	Seed values* Placebo/ Lebrikizumab 250 mg Q2W/Q4W
IGA	12345
EASI	12346
Pruritus NRS score	12347

Abbreviations: EASI = Eczema Area and Severity Index score; IGA = Investigator's Global Assessment for AD; MCMC = Markov chain Monte Carlo multiple imputation; NRS = Numeric Rating Scale; Q2W = every 2 weeks; Q4W=every 4 weeks.

6.4.2.2. Maintenance Period NRI

The nonresponder imputation (NRI) method will be used to handle missing data relative to the maintenance supportive estimand for categorical endpoints (composite). Patients who receive rescue medication (per Protocol Section 6.3), discontinue treatment, or transfer to escape arm will be set to non-response subsequent to this time through Week 52 Intermittent missing values will also be set to non-response.

Re-randomized patients without at least 1 postbaseline observation will also be defined as nonresponders for all visits for the NRI analysis.

